11.7.4. Laboratory Parameters

Clinical laboratory parameters performed at the Central Laboratory (e.g., anti-fXa activity and TG) will be summarized by time point. For patients with anti-fXa activity levels obtained by a local laboratory assay for purposes of eligibility (for patients with a time from last dose greater than 15 hours), values will be documented but not formally analyzed.

Baseline values, the values at each subsequent visit, and changes from baseline will be summarized for each of the quantitative laboratory assessments.

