10.0 STUDY ASSESSMENTS

Assessments, testing and treatment schedules are detailed in [Appendix A](#). No reference to timing or frequency is described below.

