10.3.4. Clinical Laboratory Testing

Blood specimens for routine chemistry and hematology will be obtained at selected time points (see [Appendix A](#)).

The following assays will be performed at the Local Laboratory:

- Hematology: hemoglobin, hematocrit, white blood cell (WBC) count, platelet count, WBC differential
- Coagulation: prothrombin time reported as the INR

- Serum Chemistry: sodium, potassium, chloride, carbon dioxide (bicarbonate), glucose, blood urea nitrogen, creatinine, aspartate aminotransferase, alanine aminotransferase, alkaline phosphatase, and total, direct, and indirect bilirubin
- Serum or urine pregnancy test (in women of child bearing potential; see [Appendix D](#))

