11.7. Safety Endpoints and Summaries

Safety will be assessed by examining the following endpoints and analyzed in the Safety Analysis Population:

- AEs (including SAEs), vital signs, physical examinations, and clinical laboratory measurements.
- TEs within 30 days of enrollment, including those suspected and confirmed by adjudication.
- Centrally-adjudicated deaths within 30 days of enrollment, including all-cause mortality and cardiovascular mortality.
- Antibodies to FX, FXa, andexanet, and HCPs.

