Appendix F: American Society of Anesthesiologists Physical Status Classification

Appendix G: Protocol Summary of Changes (Original vs. Amendment 1)

APPENDIX A. SCHEDULE OF ACTIVITIES

STUDY DAY:	Screening & Baseline			Treatment				Follow-Up		
				1				2	3	30 or ET
TIME POINT AND WINDOW:	-2 hours to -45 min	-45 min to -30 min	-30 min to -5 min	End of Bolus +15 min	EoII -15 min	EoS [1] + 15 min [2]	EoS + 12 h ± 1 h	EoS + 24 h ± 1 h	EoS + 72 h ± 1 h	+ 7 days
Obtain Consent	X									
Determine Eligibility	X									
Obtain Medical History	X									
Demographics	X									
Obtain Prior Medications and Time of Last Anticoagulant Dose or Plasma Level	X									
Obtain ASA Class			X							
Vital Signs (BP, HR, RR, temp)	X	X		X	X	X	X	X	X	X
Weight (actual reported/recent)	X									X
Physical Examination	X						X	X	X	X
Central Labs: Anti-fXa and anti-IIa Activity		X (pre-ADX)		X	X	X				
Central Labs: Thrombin Generation		X (pre-ADX)		X	X	X	X	X	X	
Central Labs: Antibodies to andexanet, HCPs, and FX/FXa (modified Bethesda); and nAb (andexanet)	X (pre-ADX)									X
Central Labs: TFPI activity		X (pre-ADX)		X	X	X	X	X	X	
Local Labs: PT-INR	X									

STUDY DAY:	Screening & Baseline			Treatment				Follow-Up		
				1				2	3	30 or ET
TIME POINT AND WINDOW:	-2 hours to -45 min	-45 min to -30 min	-30 min to -5 min	End of Bolus +15 min	EoII -15 min	EoS [1] + 15 min [2]	EoS + 12 h ± 1 h	EoS + 24 h ± 1 h	EoS + 72 h ± 1 h	+ 7 days
Local Labs: Chemistry and Pregnancy Test [3]	X									
Local Labs: CBC		X				X	X			X
Prepare Andexanet	X									
Administer Andexanet Bolus, Immediately Followed by an Infusion			X							
Assess Need for Extended Andexanet Infusion.(if Surgery Ongoing)					X [4]					
Surgical Intervention				SURGERY						
Record Blood Loss Post Surgery						X				
Record Investigator Assessment of Intraoperative Hemostasis						X				
Record Blood Products & Hemostatic Treatments [5]		X								
Record Bleeding-Related Diagnostic & Therapeutic Procedures [6]		X						X	X	
Record Volume of Colloid and Crystalloid [5]		X								
Record Hours in ED, PACU, ICU/Critical Care, General Hospital Floor, and Total as an Inpatient										X

STUDY DAY:	Screening & Baseline			Treatment				Follow-Up		
				1				2	3	30 or ET
TIME POINT AND WINDOW:	-2 hours to -45 min	-45 min to -30 min	-30 min to -5 min	End of Bolus +15 min	EoII -15 min	EoS [1] + 15 min [2]	EoS + 12 h ± 1 h	EoS + 24 h ± 1 h	EoS + 72 h ± 1 h	+ 7 days
Record AEs	X			X				X	X	X

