5.2 Visit Procedures (Days 1 to 30-37 , 2, 3, and 30)	The visit procedures are described in the Schedule of Activities (Appendix A).	
The visit procedures are described in the Schedule of Activities (Appendix A).
 
Day 1 Inpatient
 
On Day 1, patients will receive treatment with andexanet and will undergo the urgent surgery. Prior to start of dosing, patients will have the general health status assessed and categorized according to the American Society of Anesthesiologists Classification, repeat safety assessments (serial vital signs, repeat physical examination, and local labs). Study specific assessments and central laboratory samples will be collected to assess in vitro hemostasis.
 
The dose of andexanet will be selected based on anticoagulant product/brand, dose, and time of last dose of anticoagulant the patient is taking. The duration of the surgery will determine the total dose and duration of andexanet administered. Generally, it is planned for patients to complete the bolus and start infusion immediately prior to start of surgery and receive andexanet infusion, including extended dosing as necessary, for the duration of their surgical procedure. During the surgery, the investigator and staff will provide assessment of hemostasis and record all supporting medications related to hemostasis support. Patients should remain hospitalized on Day 1. The patient will be scheduled for study Day 2 visit.
 
Day 2 and Day 3
 
Follow-up visits on Days 2 and 3 will be conducted as an inpatient or outpatient. Patients will receive safety assessments (vital signs, physical examination, and local
	Details of procedures performed on specific days as well as rationale for dose selection have been added to the text to provide clarity.	S

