		
laboratory testing) along with collection of samples for central laboratory analysis to assess hemostasis. Diagnostic and therapeutic products supporting hemostasis will be assessed, documented and reported. Adverse events and concomitant medications will be recorded. The patient will be scheduled for study Day 30 visit.
 
Day 30
 
The Follow-up visit on Day 30 will be conducted as an inpatient or outpatient. Safety assessments will be performed (vital signs, physical examination, weight, and local laboratory testing) along with collection of samples for central laboratory analysis to assess hemostasis. Adverse events and concomitant medications will be recorded. The investigator will assess and report duration of hospitalization by unit type (emergency, critical care units, post-op units, etc.) and document the survival status of the patient.
 
Procedures performed at the Day 30 visit will also be performed for all early terminating patients (Section 5.4).
		
5.3	
During the study, additional clinical visits may be scheduled at the Investigator's discretion in order to follow or evaluate AEs. The reason for an unscheduled visit will be recorded.
 
The following must be performed at an unscheduled visit:
 
 • Record the reason for the unscheduled visit. • Record AEs since last study visit. • Record use of concomitant medication since last study visit. 	
During the study, additional clinical visits may be scheduled at the Investigator's discretion in order to follow or evaluate AEs. care for the patient. The reason for an unscheduled visit will be recorded in the eCRF.
 
The following must be performed at an unscheduled visit:
 
 • Record the reason for the unscheduled visit. • Record AEs since last study visit. • Record use of concomitant medication since last study visit. 	
Wording changed for clarity and specified additional information to be captured at unscheduled visits.
	NS

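### Section 11.7.4 promises later values and changes from baseline for every quantitative laboratory test, but Appendix A schedules serum chemistry and PT-INR only once, before andexanet

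*Protocol*

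**What the plan says.** All references are to the Amendment 1 text unless stated otherwise.

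- Section 11.7 lists, as a safety endpoint in the Safety Analysis Population: "AEs (including SAEs), vital signs, physical examinations, and clinical laboratory measurements".
- Section 11.7.4 first covers central laboratory parameters and sets aside local anti-fXa values obtained for eligibility. A separate paragraph then gives the general rule: "Baseline values, the values at each subsequent visit, and changes from baseline will be summarized for each of the quantitative laboratory assessments".
- Section 10.3.4 defines the local tests: hematology, prothrombin time as INR, and a serum chemistry panel that includes creatinine, transaminases, alkaline phosphatase and bilirubin. On timing it says "Blood specimens for routine chemistry and hematology will be obtained at selected time points" and points to Appendix A.
- Section 10.0 confirms that the assessment text sets no times of its own: "No reference to timing or frequency is described below".
- In Appendix A, the rows "Local Labs: PT-INR" and "Local Labs: Chemistry and Pregnancy Test [3" (the bracket opens a footnote mark) each have one mark, in the earliest screening column.

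**The concern.** A change from baseline needs a baseline and at least one later value. For chemistry and INR the schedule provides the first and not the second, so the analysis section commits to a summary of a named safety endpoint that the visit schedule cannot supply. A statistical analysis plan can define tables, but it cannot create samples that were never scheduled.

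At stake is the description of kidney, liver and INR values after dosing. With a single arm and no concurrent control, within-patient change is the natural way to present laboratory safety data. If later values arrive only because a clinician had a reason to test, they describe the patients who caused concern and not the treated population.

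**Working it through.** No sample size, power or error-rate figure is involved. The check is a count of scheduled draws.

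**Inputs.** The main schedule in Appendix A has 10 time columns. Columns 1 to 3 are screening, baseline and the dosing window: -2 hours to -45 min, -45 to -30 min, and -30 to -5 min. The bolus is marked in column 3. Columns 4 to 10 are post-dose: end of bolus, end of initial infusion, end of surgery (EoS), EoS + 12 h, EoS + 24 h, EoS + 72 h, and Day 30 or early termination. That gives 10 − 3 = 7 post-dose columns. The antibody row is left out because Section 11.7.7 assigns it to a listing.

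**Count of post-dose marks per quantitative row.**

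| Row | Post-dose columns marked | Count of 7 |
|---|---|---|
| Anti-fXa and anti-IIa (central) | 4, 5, 6 | 3 |
| Thrombin generation (central) | 4 to 9 | 6 |
| TFPI activity (central) | 4 to 9 | 6 |
| CBC (local) | 6, 7, 10 | 3 |
| PT-INR (local) | none (column 1 only) | 0 |
| Chemistry (local) | none (column 1 only) | 0 |

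Four rows share 3 + 6 + 6 + 3 = 18 post-dose marks; two rows have none. The separate re-dose schedule in Appendix A lists only anti-fXa and anti-IIa, so it adds nothing for chemistry or INR.

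**Is the single mark an extraction error?** The same single screening mark for both rows appears in the current Appendix A, in the two schedules reproduced in Appendix G, and in Appendix A of the original protocol. Four concordant copies make an extraction error unlikely.

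**Putting the texts together.** Section 11.7.4 calls for change from baseline on each quantitative test. Section 10.3.4 makes chemistry and INR protocol tests. Section 10.0 hands timing to Appendix A. Appendix A gives each of them one pre-dose draw. The number of schedule-based change scores per patient is therefore 0 for every chemistry analyte and 0 for INR.

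**Where blood is already drawn.** EoS + 12 h has CBC, thrombin generation and TFPI. EoS + 24 h has thrombin generation and TFPI. Day 30 has CBC and antibodies.

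**Size of the added sampling.** The protocol gives no treated number. Section 11.6 plans about 200 enrolled and 150 to 180 after attrition, so I assume 150 to 200. Chemistry at two visits: 2 × 150 = 300 to 2 × 200 = 400 samples. INR at one visit: 150 to 200 samples.

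**The case against.** **The sentence in Section 11.7.4 is a general rule, to be read as applying where a test is scheduled.** This is fair as far as it goes. Read literally, CBC would also fail, since it has no mark at EoS + 24 h or EoS + 72 h. Reading it as ‘where scheduled’ rescues CBC and the central assays, which have some post-dose samples. It does not rescue chemistry or INR, which have none.

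**Baseline-only chemistry may be deliberate.** Chemistry shares its row with the eligibility pregnancy test, the single mark survived Amendment 1, and Appendix G records that chemistry was removed from the Early Termination visit. This stands as a real possibility. If it is so, Section 11.7.4 promises too much.

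**Other text may require post-dose local tests.** The Appendix G wording for Section 5.2 mentions local laboratory testing on Days 2 and 3 ("Patients will receive safety assessments (vital signs, physical examination, and local" laboratory testing) and on Day 30 ("Safety assessments will be performed (vital signs, physical examination, weight, and local laboratory testing"). It names no analytes, and the Amendment 1 body text of Section 5.2 is not shown. Two stronger readings are tempting here. A reader might infer that post-dose chemistry and INR could come only from discretionary or event-driven testing; the documents do not establish that, because the unseen section might require some. A reader might also treat the difference between the log and Appendix A as an error in itself, or as a reason to add draws. The log is not governing text and supports neither.

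**The consequence is small.** The laboratory endpoint is not empty, clinically significant abnormalities must be reported as adverse events (Section 9.2.4.4), and the prior study in 352 bleeding patients reported no clinically meaningful laboratory change related to andexanet (original protocol, Section 1.4.7). This limits the importance of the point. It does not remove the mismatch, and event reporting depends on who was tested.

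**Conclusion.** The point holds in a limited form. Within the current protocol, the laboratory summary in Section 11.7.4 cannot be produced for serum chemistry or PT-INR from the visits that Appendix A schedules: 2 of 6 quantitative rows, each with 0 of 7 post-dose draws. CBC, the central assays and all efficacy analyses are unaffected.

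The conclusion rests on Appendix A governing timing, as Section 10.0 says, and on reading its columns correctly, which the four concordant copies support. It does not show that no post-dose chemistry or INR values will exist. Nor does it show a hidden kidney or liver signal; the documents describe none. Even with added draws, a change measured after surgery in a single arm would be descriptive and could not separate andexanet from the operation.

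It should be corrected: the mismatch is plain, it concerns a named safety endpoint, and the remedy is cheap.

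**What to change.** In Appendix A, mark local chemistry and INR at one early post-operative visit where blood is already drawn, either EoS + 12 h or EoS + 24 h, and mark chemistry again at Day 30 alongside the existing CBC draw. A Day 30 INR is not needed: many patients are likely to have resumed anticoagulation by then, and that would confound it.

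The cost is one or two extra local tubes per patient at draws that already take place: about 300 to 400 chemistry samples and 150 to 200 INR samples, on the assumed 150 to 200 treated patients.

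If baseline-only sampling is intended, limit the sentence in Section 11.7.4 to tests with scheduled post-dose samples and report chemistry and INR as baseline descriptors. That costs one sentence and makes the protocol consistent, but adds no safety information.

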11.7.5. Vital Signs

Vital signs will be summarized using actual values and change from baseline at pre-specified time points for each treatment group. Descriptive statistics, including threshold-based outlier analyses, will be presented.

11.7.6. Physical Examinations

Findings on physical examination will be summarized in a listing.

11.7.7. Antibodies

The presence of antibodies (anti-andexanet, anti-fX, anti-fXa, anti-HCPs, and/or nAb activity) will be summarized in a listing.

11.8. Interim Analyses

During the conduct of the study, interim monitoring of safety data by the DSMB will commence after 50 patients are enrolled, then performed periodically at a frequency of approximately every 6 months. Additional interim analyses of efficacy and/or safety data may be performed during the study to support regulatory and/or business objectives (such as informing future study designs). No adjustment to the type I error rate or CI coverage will be made to account for interim analyses. Details of the interim analysis and its review process will be described in the DSMB Charter.

11.9. Subgroup Analyses

Consistency of efficacy across important subgroups will be investigated within each cohort. At a minimum, primary efficacy will be summarized for subgroups of sex (male, female), race (any race with at least 5 members, all others combined), age (< 65 years, \geq 65 years, \geq 75 years), anticoagulant, baseline anti-fXa activity categories (e.g., above and below thresholds of 30 ng/mL, 50 ng/mL, 75 ng/mL), procedure type (e.g., orthopedic, abdominal, thoracic, neurosurgical), duration of surgery (\leq 2 hours, 2-4 hours, $>$ 4 hours), and volume of blood loss (above and below the median). Other subgroup analysis may be considered based on the actual enrollment. Further detail of the subgroup analysis will be described in the Statistical Analysis Plan.

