11.3.3. Efficacy Analysis Population

The efficacy analysis population will include all enrolled patients who receive any amount of andexanet treatment, undergo surgery, and have a baseline anti-fXa activity analyzed by central laboratory at or above the evaluability threshold (75 ng/mL for apixaban, edoxaban and rivaroxaban, and 0.25 IU/mL for enoxaparin).

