11.5.3. Statistical Methodology for Endpoint Analyses

All efficacy analyses will be performed on the efficacy analysis population. All hypothesis tests and CIs will be 2-sided with $\alpha=0.05$.

The primary endpoint, the proportion of patients who have effective hemostasis, will be summarized with a 95% CI.

The secondary endpoint, percent change in anti-fXa activity from baseline to the nadir for the evaluation period, will be assessed with a 2-sided 95% nonparametric CI for the median.

For the exploratory endpoints, counts data will be summarized by observed rates and associated 95% CIs. Continuous endpoints will be summarized by means or medians and associated 95% CIs.

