11.6. Determination of Sample Size

Approximately 200 patients will be enrolled. After accounting for 10 to 25% attrition (e.g., canceled surgeries, discontinued and/or non-evaluable patients, or baseline anti-fXa activity analyzed by central laboratory less than the evaluability threshold), a sample size of 150 or 180 patients will provide an estimate of the proportion of achieving effective (excellent or good) hemostasis with a margin of error (half width of the 95% confidence interval) that is less than 8% or 7.3%, respectively. Additionally, with 150 to 180 patients, there will be 78% to 84% chance to observe a rare event with 1% occurrence rate.

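### The baseline anti-fXa cut-points named in Section 11.9 (30, 50 and 75 ng/mL) cannot divide the efficacy population, which for the oral inhibitors starts at 75 ng/mL

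*Protocol*

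**What the plan says.** All references are to the amended protocol text unless stated otherwise.

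- **Section 11.9** sets a minimum list of subgroups: "At a minimum, primary efficacy will be summarized for subgroups of sex (male, female"), and so on through race, age and anticoagulant to "baseline anti-fXa activity categories (e.g., above and below thresholds of 30 ng/mL, 50 ng/mL, 75 ng/mL"). It names no analysis population for these summaries and leaves further detail to the statistical analysis plan.
- **Section 11.3.3** requires a patient in the Efficacy Analysis Population to have a central-laboratory baseline "at or above the evaluability threshold (75 ng/mL for apixaban, edoxaban and rivaroxaban, and 0.25 IU/mL for enoxaparin").
- **Section 11.5.3** states: "All efficacy analyses will be performed on the efficacy analysis population". It makes no exception for subgroups.
- **Section 11.6** lists among the causes of attrition a "baseline anti-fXa activity analyzed by central laboratory less than the evaluability threshold".

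**The concern.** The three sections cannot all be followed as written. A programmer who applies the named cut-points to the population that Section 11.5.3 prescribes will produce three tables in which one column is empty and the other repeats the overall result. One who widens the population so that the lower columns fill will depart from Section 11.5.3.

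The study has a single arm, so comparisons inside the trial carry more weight than usual. Baseline drug level is a natural one to make: it helps to show whether good hemostasis goes with reversal of a substantial anticoagulant effect or is also seen when little inhibitor was present. The named splits cannot contribute to that question.

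The likely origin is an edit that was not carried through. The original protocol, which is in the same file, had the same three cut-offs but put no anti-fXa threshold on its efficacy population. The amendment added the threshold and left the numbers in Section 11.9. This is background only; the conflict lies within the amended text.

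**Working it through.** **1. The plan's own figures (Section 11.6).** The inputs are about 200 enrolled and 10 to 25% attrition.

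- Evaluable patients: 200 × (1 − 0.10) = 180; 200 × (1 − 0.25) = 150.
- 95% half width, 1.96 × √(0.25/n), at a proportion of 0.5: n = 150 gives 8.00%; n = 180 gives 7.30%.
- Chance of seeing at least one event of 1% frequency, 1 − 0.99ⁿ: n = 150 gives 77.9%; n = 180 gives 83.6%.

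To rounding, these match the stated 8%, 7.3%, 78% and 84%. None of them depends on the subgroup cut-points.

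**2. The subgroup cut-points against the population.** For apixaban, edoxaban and rivaroxaban, let x be the central-laboratory baseline. Membership requires x ≥ 75 ng/mL. The lower group at cut-point t requires x < t.

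| Cut-point t | Patients with x ≥ 75 and x < t | Share with x ≥ t |
|---|---|---|
| 30 ng/mL | 0 | 100% |
| 50 ng/mL | 0 | 100% |
| 75 ng/mL | 0 | 100% |

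This follows from the definitions and holds for any enrolment. A value of exactly 75 counts as evaluable and so belongs with the upper group.

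**3. Whether anything else could fill the lower groups.**

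- *Enoxaparin.* Entry is at 0.25 IU/mL. Values in IU/mL have no place on ng/mL cut-points.
- *Local laboratory values.* They serve eligibility, where they must exceed 100 ng/mL for the ng/mL route (Sections 10.1.5 and 10.2.1), and Section 11.7.4 excludes them from formal analysis.
- *A wider population.* Section 11.9 does not name one, and using one would conflict with Section 11.5.3.

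**4. How large a below-threshold group could be.** Section 11.6 allows 20 (200 × 0.10) to 50 (200 × 0.25) patients lost to all causes together. Canceled surgery, discontinuation and non-evaluability share that allowance with low baselines, so the sub-threshold number is unknown. As an illustration only, if all 50 were treated, operated and sub-threshold, the half width at a proportion of 0.5 would be 1.96 × √(0.25/50) = 13.9%. With 20 it would be 1.96 × √(0.25/20) = 21.9%. Within the plan's allowance, then, even the most favorable case gives an imprecise estimate.

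**The case against.** The best reply is that the cut-points are only examples. The amendment itself loosened this clause: the original protocol fixed the three cut-offs, whereas the current text introduces them with an e.g. and refers to the statistical analysis plan. What is required is a summary by baseline category, and any cut-point above 75 ng/mL would meet that without conflict. This stands as a limit on the point's force. It does not remove the point, because every example given is unusable and the only way to use them contradicts Section 11.5.3.

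A reader might also infer more than the documents support:

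- *That the required subgroup must come back empty.* It need not, since the analysis plan can choose other cut-points.
- *That all view of how hemostasis depends on drug level is lost.* Section 11.5.2.3 keeps an exploratory look at how intraoperative hemostasis relates to anti-fXa activity. It runs on the same restricted population, so what is missing is the comparison with patients below the threshold.
- *That leaving sub-threshold patients out of efficacy is itself an error.* It is a stated design choice, allowed for in Section 11.6, and it keeps low baselines out of the primary estimate.
- *That the cited bleeding study gives the size.* Section 1.4.7 of the original protocol text reports 254 of 352 as efficacy-evaluable, leaving 98 (98/352 = 27.8%). That rule also required an adjudicated major bleed, and no breakdown is given.
- *That the 25% attrition gives the size.* It pools several causes.

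**Conclusion.** The point holds as an inconsistency in the current text. For patients on the three oral inhibitors, the named splits at 30, 50 and 75 ng/mL give 0 patients below and 100% at or above, whatever the enrolment, and for enoxaparin the cut-points have no meaning. This rests on reading Section 11.5.3 as covering the subgroup summaries of primary efficacy, which its wording supports.

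The consequence is modest. One descriptive subgroup is uninformative if run with the cut-points named. The primary proportion, its confidence interval, the sample size and the safety summaries are untouched. The correction is still worth making because it is almost free and turns an empty table into a usable one.

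**What to change.** Amend Section 11.9, or settle it in the statistical analysis plan with a matching note, in one or both of these ways:

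1. Replace the cut-points with values above 75 ng/mL for the oral inhibitors, and give enoxaparin separate categories in IU/mL.
2. State, as an explicit exception to Section 11.5.3, that the baseline anti-fXa summary is run on all patients who received andexanet and had surgery, whatever their baseline. Use a single split, below versus at or above the evaluability threshold (75 ng/mL, or 0.25 IU/mL for enoxaparin). Finer strata below the threshold would be too sparse.

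Choose the cut-points before results are seen. The cost is wording and one descriptive table. No new data are needed: Appendix A already schedules a pre-dose central sample, and Section 12.0 has hemostatic efficacy adjudicated for every patient. The drawback of the second option is that the below-threshold group may be small, so its estimate should be shown with its interval and read as descriptive.

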10.4.2. Intraoperative Blood Loss

Investigators will report blood loss during surgery for each patient. Blood loss will be reported as an estimate of blood loss in milliliters. Blood loss will be reported at the end of surgery. It is an intraoperative assessment and will not be updated for post-closure blood loss.

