11.5. Efficacy Endpoints and Analyses

11.5.1. Definitions

Hemostasis will be assessed from the start of surgery to the end of the procedure. Categories for the assessment of intraoperative hemostasis are provided in Table 3.

Table 3: Intraoperative Hemostasis Categories

Category	Definition
Excellent	Normal hemostasis during the procedure
Good	Mildly abnormal hemostasis as judged by quantity or quality of blood loss (e.g., slight oozing from surgical wounds)
Moderate	Moderate abnormality in intraprocedural hemostasis (e.g., controllable bleeding) but no need for additional systemic procoagulant products *
Poor	Severe hemostatic abnormality during the procedure (e.g., severe refractory hemorrhage) and need for additional systemic procoagulant products *

* Tranexamic acid excluded.

The evaluation period for anti-fXa activity covers the period of time from 5 minutes following the end of the andexanet bolus to just prior to the end of the andexanet infusion. The baseline measurement will be the last value obtained prior to andexanet treatment.

The hemostasis evaluation would exclude unexpected blood loss due to surgical complications that may cause uncontrolled bleeding, such as unintended injury of a major vessel or parenchymal tissue.

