4.2. Exclusion Criteria

If a patient meets any of the following criteria, he or she is *not* eligible to participate:

1. Surgery predicted to last > 4 hours or for which the risk of clinically meaningful uncontrolled or unmanageable bleeding is low.
2. Acute life-threatening bleeding at the time of Screening.
3. Any surgical procedure requiring cardiopulmonary bypass, an intra-aortic catheter, or the intra-operative use of systemic, intravascular, unfractionated heparin.
4. Expected survival of < 1 month due to comorbidity.
5. Existing “Do Not Resuscitate” order or similar advanced directive.
6. The patient has a recent history (within 30 days prior to Screening) of a diagnosed TE as follows: VTE (including DVT, PE, intracardiac thrombus); myocardial infarction (including asymptomatic troponin elevations); disseminated intravascular coagulation (DIC); acute traumatic coagulopathy; cerebrovascular accident; transient ischemic attack; unstable angina pectoris hospitalization; or severe peripheral vascular disease (see [Appendix B](#) for DIC scoring algorithm).
7. Acute decompensated heart failure or cardiogenic shock at the time of screening (see [Appendix C](#) for cardiogenic shock definition)

8. The patient has severe sepsis or septic or hemorrhagic shock at the time of Screening (see definition in [Appendix C](#)).
9. The patient is pregnant or a lactating female.
10. The patient has received any of the following drugs or blood products within 7 days of enrollment:
 - VKA (e.g., warfarin).
 - Dabigatran.
 - Prothrombin complex concentrate products (PCC, e.g., Kcentra[®]), recombinant factor VIIa (rfVIIa) (e.g., NovoSeven[®]).
 - Whole blood, plasma fractions.
 - Note: Administration of tranexamic acid (TXA), platelets, or packed red blood cells (PRBCs) is not an exclusion criterion.
11. The patient was treated with an investigational drug < 30 days prior to Screening.
12. Prior treatment with andexanet.

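### Volume of blood loss is listed as a subgroup for consistency of primary efficacy, but it overlaps with the endpoint itself, so the split cannot inform consistency

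*Protocol*

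**What the plan says.** Section 11.9 (Amendment 1 text) states its aim as "Consistency of efficacy across important subgroups will be investigated within each cohort". It commits, as a minimum, to summarizing primary efficacy by sex, race, age, anticoagulant, baseline anti-fXa activity, "procedure type (e.g., orthopedic, abdominal, thoracic, neurosurgical), duration of surgery" (three bands), "and volume of blood loss (above and below the median". Further detail is left to the SAP, but these splits are already fixed.

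Three other places matter:

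- Section 10.4.2: blood loss is an investigator's estimate in milliliters for the operation. "Blood loss will be reported at the end of surgery".
- Section 11.5.1: "Hemostasis will be assessed from the start of surgery to the end of the procedure". Table 3 defines the Good grade as "Mildly abnormal hemostasis as judged by quantity or quality of blood loss". The same section leaves unexpected blood loss from surgical complications out of the hemostasis evaluation.
- Section 11.5.2.1: Excellent and Good count as effective, Moderate and Poor as ineffective. The surgeon's assessment is confirmed by the independent adjudication committee.

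On duration, Section 4.2 excludes "Surgery predicted to last > 4 hours or for which the risk of clinically meaningful uncontrolled or unmanageable bleeding is low". That section is available only in its original-protocol form, but the revised column of Appendix G keeps the criterion.

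**The concern.** A consistency subgroup should be defined by something that does not depend on the outcome being compared. Sex, anticoagulant and procedure type meet that test. Blood loss does not: it accrues while the endpoint is being determined, and its quantity is a named criterion for the grade just on the effective side of the cut.

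The trial has a single arm (Section 11.2), so no control contrast within each half could separate sorting on the outcome from a true difference in drug effect. A reader shown a lower effective-hemostasis rate in the higher-loss half, under the label of consistency, could conclude that the drug works less well in bloodier operations. The table could not support that conclusion. Section 11.9 carries no caution on this point.

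**Working it through.** **The plan's own figures.** Section 11.6 plans on 150 to 180 evaluable patients from 200 enrolled: 200 × 0.75 = 150 and 200 × 0.90 = 180. Its half widths reproduce at a proportion of 0.5: 1.96 × √(0.25/150) = 0.080 and 1.96 × √(0.25/180) = 0.073. The protocol gives no figure for the subgroup analysis. A median split leaves 75 to 90 patients per half.

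**Overlap of the two measures.**

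| | Blood loss | Primary endpoint |
|---|---|---|
| Period | The operation (10.4.2) | Start of surgery to end of procedure (11.5.1) |
| Recorded | End of surgery (10.4.2, Appendix A) | End of surgery (Appendix A), then adjudicated |
| Content | Estimated volume | Grade; Good is judged by quantity or quality of blood loss |
| Complication bleeding | No exclusion stated | Excluded from the evaluation |

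**Size of the gap under a uniform drug effect.** Let hemostatic abnormality and blood loss (on a suitable scale) be standard bivariate normal with correlation ρ. Hemostasis is effective when abnormality falls below c = Φ⁻¹(p), where p is the overall rate. Then:

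- rate below the median = Φ₂(c, 0; ρ) / 0.5
- rate above the median = (p − Φ₂(c, 0; ρ)) / 0.5

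For any ρ > 0, Φ₂(c, 0; ρ) exceeds p/2, so the lower-loss half always does better.

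Inputs: p = 0.82 is an assumption for this trial, taken from the earlier study in bleeding patients (Section 1.4.7: 204/249 = 81.9%). The values of ρ are assumptions; the protocol gives none.

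| Assumed ρ | Below median | Above median | Gap (points) | Chance of nominal p < 0.05, N = 150 / 180 |
|---|---|---|---|---|
| 0 | 82.0% | 82.0% | 0 | – |
| 0.2 | 86.2% | 77.8% | 8 | 27% / 31% |
| 0.3 | 88.3% | 75.7% | 13 | 52% / 60% |
| 0.5 | 92.5% | 71.5% | 21 | 93% / 96% |

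The last column is for scale only, since no subgroup test is planned. With no gap, the 95% CI half width in each half is 1.96 × √(0.82 × 0.18/75) = 8.7 points, or 7.9 points with 90 patients. The artificial gap is thus about the size of that half width at ρ = 0.2 and well beyond it at 0.5.

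**Sensitivity to the overall rate, at ρ = 0.5.** At p = 0.77 the rates are 89.3% and 64.7% (25 points). At p = 0.90 they are 96.8% and 83.2% (14 points).

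**The case against.** The strongest reply is that nothing rests on this table. Section 11.9 only summarizes, with no interaction test, threshold or decision rule, and the primary analysis is a proportion with a 95% CI (Section 11.5.3). That stands: a reader might infer that the primary result is compromised, and it is not.

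The link between the two measures may also be weak. Quantity appears only in the Good row, alongside quality, and the effective/ineffective boundary is not a volume cut-off. Complication bleeding is excluded from the grade but not from the recorded volume, so the measures diverge where losses may be largest. This bears on the size of the gap, which is why it is shown over a range of correlations. It does not turn blood loss into a baseline factor.

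It can further be said that, in a single arm, any prognostic factor gives different rates under a uniform effect. This is true, and procedure type may do so too. The difference is that procedure type describes patients before treatment, while blood loss sorts them by part of what is being measured.

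Two stronger readings are tempting but not supported:

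- **One person records both measures.** Section 10.4.2 has investigators report blood loss. Section 11.5.2.1 has the surgeon assess hemostasis and an independent committee confirm it.
- **Observed duration is a consequence of poor hemostasis and should also go.** No section says that poor hemostasis prolongs surgery, and duration also reflects the procedure. It has its own relevance, because whether surgery outlasts the initial course determines whether the infusion is extended (Section 6.2). What does stand is that duration is known only at skin closure, and that the stratum above 4 hours can hold only operations that overran their prediction.

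**Conclusion.** The point holds for volume of blood loss. The variable is post-treatment, covers the same operation as the endpoint, and is one of the criteria by which the endpoint is graded. Splitting on it cannot inform consistency, whatever the table shows.

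The direction of the artefact needs only a positive correlation. Its size depends on values the protocol does not give: about 8 to 21 points for assumed correlations of 0.2 to 0.5 at an overall rate of 82%. It would be wrong to say that large false heterogeneity must appear; at a low correlation the gap is modest. The consequence is a misleading secondary table. The primary estimate and the sample size are unaffected. For observed duration the issue is one of labelling only.

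**What to change.** In Section 11.9, remove volume of blood loss from the consistency subgroups. Report observed blood loss by the four hemostasis categories instead, described as an association between two intraoperative measures.

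Keep observed duration if wanted, but label it post-baseline and descriptive, and note that the stratum above 4 hours can contain only operations that exceeded the predicted-duration limit. Procedure type, already listed, serves as the pre-treatment surgical subgroup.

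The cost is a wording change in the protocol or SAP, with no new data collection. The downside is that one subgroup table becomes a descriptive cross-tabulation.
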